10 EVALUATIONS BY VISIT

See Appendix 1.

10.1 Visit 0 (Screening)

1. Review inclusion/exclusion criteria.
2. Review the study with the subject and obtain written informed consent and HIPAA authorization and assent, if appropriate.
3. Assign the subject a unique screening number.
4. Record demographics data.
5. Record medical history, including a history of atopic dermatitis, diagnosis date, and prior treatments for atopic dermatitis.
6. Record concomitant medications.
7. Perform and record vital signs.
8. Perform a complete physical examination.
9. Perform EASI and IGA.

10. Perform pruritus numerical rating.
11. Collect blood for clinical laboratory tests (CBC, serum electrolytes, BUN, Creatinine, AST, ALT, alkaline phosphatase).
12. Perform urine pregnancy test (if applicable).

10.2 Visit 1: PRE-TREATMENT PATCH TESTING

1. Application of contact allergens (20 minutes).
2. 48 hours later: removal of allergens and photography (30 minutes).
3. 120 hours later: final reading of allergens (10 minutes) and allergen avoidance counseling (approximately 30 minutes).

10.3 Visit 2 (week 0)

1. Record any Adverse Experiences.
2. Concomitant medications review.
3. Perform and record vital signs.
4. Perform a complete physical examination.
5. Perform EASI and IGA.
6. Perform pruritus numerical rating.
7. Perform urine pregnancy test (if applicable).
8. Perform skin biopsy procedure.
9. Obtain photographs.
10. Dispense study medication.
11. Collect skin swabs and stool sample.

10.4 Visit 3 (week 2)

1. Record any Adverse Experiences.
2. Concomitant medications review.
3. Perform and record vital signs.
4. Perform EASI and IGA.
5. Perform pruritus numerical rating.
6. Perform skin biopsy procedure.
7. Obtain photographs.
8. Dispense study medication.
9. Collect skin swabs and stool sample.

10.5 Visit 4 (week 4)

1. Record any Adverse Experiences
2. Concomitant medications review.
3. Perform and record vital signs.
4. Perform EASI and IGA.
5. Perform pruritus numerical rating.
6. Perform urine pregnancy test (if applicable).

7. Perform skin biopsy procedure.
8. Obtain photographs.
9. Dispense study medication.
10. Collect skin swabs and stool sample.

10.6 Visit 5 (week 8)

1. Record any Adverse Experiences.
2. Concomitant medication review.
3. Perform and record vital signs.
4. Perform EASI and IGA.
5. Perform pruritus numerical rating.
6. Perform urine pregnancy test (if applicable).
7. Dispense study medication.

10.7 Visit 6 (week 12)

1. Record any Adverse Experiences.
2. Concomitant medications review.
3. Perform and record vital signs.
4. Perform a complete physical examination.
5. Perform EASI and IGA.
6. Perform pruritus numerical rating.
7. Perform urine pregnancy test (if applicable).
8. Perform skin biopsy procedure.
9. Obtain photographs.
10. Dispense study medication.
11. Collect skin swabs and stool sample.

10.8 Visit 7 (week 16)

1. Record any Adverse Experiences.
2. Concomitant medications review.
3. Perform and record vital signs.
4. Perform EASI and IGA assessments.
5. Perform pruritus numerical rating.
6. Perform urine pregnancy test (if applicable).
7. Dispense study medication.

10.9 Visit 8 (week 24)

1. Record any Adverse Experiences.
2. Concomitant medications review.
3. Perform and record vital signs.
4. Perform a complete physical examination.
5. Perform EASI and IGA.

6. Perform pruritus numerical rating.
7. Perform urine pregnancy test (if applicable).
8. Dispense study medication

10.10 Visit 9 POST-TREATMENT PATCH TESTING (between weeks 24 and 36)

1. Application of contact allergens (20 minutes).
2. 48 hours later: removal of allergens and photography (30 minutes).
3. 120 hours later: final reading of allergens (10 minutes) and allergen avoidance counseling (approximately 30 minutes).

10.11 Visit 10 (week 36)

1. Record any Adverse Experiences.
2. Concomitant medications review.
3. Perform and record vital signs.
4. Perform EASI and IGA.
5. Perform pruritus numerical rating.
6. Perform urine pregnancy test (if applicable).
7. Dispense study medication.

10.12 Visit 11 (week 44)

1. Record any Adverse Experiences.
2. Concomitant medications review.
3. Perform and record vital signs.
4. Perform EASI and IGA.
5. Perform pruritus numerical rating.
6. Perform urine pregnancy test (if applicable).
7. Dispense study medication.

10.13 Visit 12: END OF TREATMENT (week 52)

1. Record any Adverse Experiences.
2. Concomitant medications review.
3. Perform and record vital signs.
4. Perform a complete physical examination.
5. Perform EASI and IGA.
6. Perform pruritus numerical rating.
7. Perform urine pregnancy test (if applicable).
8. Obtain photographs.
9. Collect skin swabs and stool sample.

10.14 EARLY WITHDRAWAL / TERMINATION VISIT

1. Record any Adverse Experiences.

2. Concomitant medications review.
3. Perform and record vital signs.
4. Perform a complete physical examination.
5. Perform EASI and IGA.
6. Perform pruritus numerical rating.
7. Perform urine pregnancy test (if applicable).
8. Obtain photographs.

For healthy controls:

- 1) Clinical consent will be obtained prior to surgery by the surgeon or their research coordinator for surgical tissue that will be resected for clinical purposes and will otherwise be discarded.
- 2) The surgeon will notify our technician the day before samples are collected
- 3) On the day of surgery, redundant skin will be obtained in the operating room.
- 4) The samples will be de-identified at the time of harvest.
- 5) The surgeon will call our technician (after the samples have been harvested and de-identified) to let them know to come to the operating room suite to pick up the samples.
- 6) The samples will be transported by our technician from outside the operating room to the lab in a biohazard-labeled container.
- 7) In the lab, the samples will be given a unique identifier that is unknown to the surgical team. Thus, there will be no way for the surgical team to identify which sample came from which patient and there is no way for the laboratory team to know any patient information about the samples. This is in accordance with an agreement stating that the individual providing the specimen will never provide the recipient research team with identifiable information.

11 ADVERSE EXPERIENCE REPORTING AND DOCUMENTATION

11.1 Adverse Events

Definition of an AE: Any untoward medical occurrence in a subject administered a pharmaceutical product that does not necessarily have a causal relationship with the treatment. An AE can therefore be any unfavorable and unintended sign (including an abnormal laboratory finding), symptom, or disease temporally associated with the use of a medicinal (investigational) product, whether or not considered related to the investigational medicinal product.

Investigational Medicinal Product (IMP) includes the drug under evaluation and the comparator drug(s) if specified as part of the research objective, given at any time during the study. Medical conditions/diseases present before starting the drug of interest are only considered adverse events if they worsen after starting the drug of interest.

The occurrence of adverse events will be sought by non-directive questioning of the patient at each visit during the study. Adverse events also may be detected when they are volunteered by the patient during or between visits or through physical examination, laboratory test, or other assessments. All adverse events will be recorded in the study database including the following information:

1. the severity grade (mild, moderate, severe)
2. its relationship to the drug(s) of interest (suspected/not suspected)
3. its duration (start and end dates or if continuing at final exam)
4. whether it constitutes a serious adverse event (SAE)

AE Severity

The National Cancer Institute's Common Terminology Criteria for Adverse Events (CTCAE) Version 3.0 should be used to assess and grade AE severity, including laboratory abnormalities judged to be clinically significant. The modified criteria can be found in the study manual. If the experience is not covered in the modified criteria, the guidelines shown in below should be used to grade severity. It should be pointed out that the term "severe" is a measure of intensity and that a severe AE is not necessarily serious.

Table 1. AE Severity Grading

Severity (Toxicity Grade)	Description
Mild (1)	Transient or mild discomfort; no limitation in activity; no medical intervention or therapy required. The subject may be aware of the sign or symptom but tolerates it reasonably well.
Moderate (2)	Mild to moderate limitation in activity, no or minimal medical intervention/therapy required.
Severe (3)	Marked limitation in activity, medical intervention/therapy required, hospitalizations possible.
Life-threatening (4)	The subject is at risk of death due to the adverse experience as it occurred. This does not refer to an experience that hypothetically might have caused death if it were more severe.

Table 2. AE Relationship to Study Drug

Relationship to Drug	Comment
Definitely	Previously known toxicity of agent; or an event that follows a reasonable temporal sequence from administration of the drug; that follows a known or expected response pattern to the suspected drug; that is confirmed by stopping or reducing the dosage of the drug; and that is not explained by any other reasonable hypothesis.
Probably	An event that follows a reasonable temporal sequence from administration of the drug; that follows a known or expected response pattern to the suspected drug; that is confirmed by stopping or reducing the dosage of the drug; and that is unlikely to be explained by the known characteristics of the subject's clinical state or by other interventions.

Possibly	An event that follows a reasonable temporal sequence from administration of the drug; that follows a known or expected response pattern to that suspected drug; but that could readily have been produced by a number of other factors.
Unrelated	An event that can be determined with certainty to have no relationship to the study drug.

11.2 Serious Adverse Experiences (SAE)

A SAE is any untoward medical occurrence that at any dose:

- results in death,
- is life-threatening,
- requires inpatient hospitalization or prolongation of existing hospitalization,
- results in persistent or significant disability/incapacity,
- is a congenital anomaly/birth defect,
- is otherwise a significant medical event.

This includes any SAEs likely to arise from the trial indication or progression of underlying/concomitant illness(es) (e.g. progression of cancer in oncology trials), unless specified in the protocol as study specific exemptions.

Any SAE, irrespective of causality, occurring after the subject has provided informed consent and until four weeks after the subject has stopped study participation must be reported unless otherwise stated in the protocol. SAEs occurring after four weeks from ending study participation should only be reported if considered by the Investigator attributable to the exposure to the investigational drug(s) during the trial period. This includes the period in which the study protocol interferes with the standard medical treatment given to a subject, even if study treatment has not yet started (e.g. withdrawal of previous treatment during washout period, change in treatment to a fixed dose of concomitant medication).

11.3 Serious Adverse Experience Reporting

Study sites will document all SAEs that occur (whether or not related to study drug) per [UCSF IRB Guidelines](#). The collection period for all SAEs will begin after informed consent is obtained and end after procedures for the final study visit have been completed.

SAEs occurring after four weeks from ending study participation should only be reported if considered by the Investigator attributable to the exposure to the investigational drug(s) during the trial period. This includes the period in which the study protocol interferes with the standard medical treatment given to a subject, even if study treatment has not yet started (e.g. withdrawal of previous treatment during washout period, change in treatment to a fixed dose of concomitant medication).

In accordance with the standard operating procedures and policies of the local Institutional Review Board (IRB)/Independent Ethics Committee (IEC), the site investigator will report SAEs to the IRB/IEC.

Timelines: All serious adverse events (SAEs) must be reported by the sites to Sponsor within 24 hours of occurrence of the SAE. The timelines for investigator initiated trials reporting to Regeneron Pharmaceuticals and Sanofi-Genzyme will be done as per Third Party Study/Investigator Initiated Trial Agreement.

Follow-up reports: SAEs will be followed until resolution or until it is judged to be permanent, and an assessment will be made at each visit (or more frequently, if necessary) of any changes in severity, the suspected relationship to the drug of interest, the interventions required to treat it, and the outcome.

The Sponsor shall support Regeneron and Sanofi-Genzyme in the following-up of all SAEs so that complete information is available to maintain patient safety and also as part of any commitments by Regeneron and Sanofi-Genzyme to any Health authority OR specific Health authority follow-up requests for the product under investigation.

Pregnancies: Any occurrences of a pregnancy in a patient (or a patient's partner) during study participation will be collected. All pregnancies will be followed up to determine outcome, including spontaneous or voluntary termination, details of the birth, and the presence or absence of any birth defects, congenital abnormalities, or maternal and/or newborn complications.

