4 STUDY DESIGN

4.1 Study Overview

This is a single center, open-label study. Fifteen subjects with moderate to severe AD will receive dupilumab for a treatment period of 52 weeks (i.e. last injection on week 48). Surgical discard specimens will also be collected from fifteen healthy subjects. Biopsy samples from AD subjects and surgical discard samples will undergo molecular profiling. Skin swabs and stool samples will be collected and banked for future analysis. **The reason to treat patients for 52 weeks is to have the ability to correlate early molecular events with clinical outcomes (EASI, IGA, itch score) at week 52. In addition, collection of microbiome samples will be performed at week 52.** See Flowchart for timeline of study activities.

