8.4 Administration Instructions

All doses of study treatment will be administered at the study site after the study assessments for the visit have been completed at visits occurring between week 0 and 4, as well as weeks 8, 12, 16, 24, 36, and 44. After week 4 subjects will administer the medication independently every other week (weeks 6, 10, 14, 18, 20 22, 26, 28, 30, 32, 34, 38, 40, 42, 46, 48, and 50) only after they have shown the competency to self-administer the treatment outside of the study site. The medication will be administered via subcutaneous injection into the thigh or abdomen, except for the 2 inches (5 cm) around the navel. The upper arm can also be used if a caregiver administers the injection. There will be no medication given after week 50.

The subject should be instructed to contact the investigator if he/she is unable for any reason to attend a study visit as scheduled. All dates and times of injections done to the subject during the study must be recorded on the Dosage Administration Record CRF. The investigator will promote compliance by instructing the subject to attend the study visits as scheduled and by stating that compliance is necessary for the subject's safety and the validity of the study.

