14 STATISTICAL METHODS AND CONSIDERATIONS

Prior to the analysis of the final study data, a detailed Statistical Analysis Plan (SAP) will be written describing all analyses that will be performed. The SAP will contain any modifications to the analysis plan described below.

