14.3 Safety Data

Safety and tolerability data will be summarized for the treatment group, which is the 15 subjects who receive treatment with dupilumab.

Adverse event rates will be coded by body system and MedDra classification term. Adverse events will be tabulated and will include the number of patients for whom the event occurred, the rate of occurrence, and the severity and relationship to study drug.

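### Section 11.3 closes collection of all SAEs at the final visit, while section 11.2 requires every SAE to be reported for four more weeks

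*Combined protocol and SAP*

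**What the plan says.** Section 11.2 defines which SAEs must be reported: "Any SAE, irrespective of causality, occurring after the subject has provided informed consent and until four weeks after the subject has stopped study participation". It allows for exceptions stated elsewhere in the protocol. Beyond the four weeks, only events that the investigator attributes to the study drug are reportable.

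Section 11.3 first tells sites to document all SAEs, related or not, under the institution's IRB guidelines. It then sets the window: "The collection period for all SAEs will begin after informed consent is obtained and end after procedures for the final study visit" have been carried out. Its next paragraph repeats the later boundary: "SAEs occurring after four weeks from ending study participation should only be reported if considered by the Investigator attributable" to the study drug.

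The last scheduled visit is Visit 12 at week 52 (section 10.13), and Appendix 1 lists no later contact. On the last dose, section 8.4 says "There will be no medication given after week 50", while section 4.1 says "Fifteen subjects with moderate to severe AD will receive dupilumab for a treatment period of 52 weeks (i.e. last injection on week 48").

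On analysis, section 14.3 says "Safety and tolerability data will be summarized for the treatment group, which is the 15 subjects who receive treatment with dupilumab". It gives no time window for events. Section 14 says that "a detailed Statistical Analysis Plan (SAP) will be written describing all analyses that will be performed" before the final data are analysed.

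**The concern.** Two adjacent sections give different end points for the same safety data. Under 11.2 an SAE three weeks after the week 52 visit must be reported whatever its cause. Under the collection sentence of 11.3 it falls outside the period in which SAEs are collected.

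The events concerned come soon after the last dose. A site that works from 11.3, the section on how to report, could reasonably close its SAE records at Visit 12. The SAE counts in the safety summary would then depend on which section the site followed, and section 14.3 does not say which events belong in the summary. SAEs must also reach the sponsor within 24 hours, so the site needs one clear window while the study is running, not a choice made at analysis.

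**Working it through.** The plan has no figure of its own to reproduce on this point. The check compares the texts and then does simple arithmetic on the ends of the windows.

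**Inputs**

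- End of SAE reporting under 11.2: four weeks after participation stops.
- End of SAE collection under 11.3: completion of the final visit.
- Final visit for a completer: week 52 (10.13, Appendix 1).
- Last dose: week 50 (8.3, 8.4, 14.4) or week 48 (4.1). Both are carried through; these passages need reconciling separately.
- Treated subjects: 15 (14.3, 14.4).
- Assumption: participation ends at the week 52 visit.

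**Step 1: is 11.3 the exception that 11.2 allows for?** If it were, all-cause collection would stop at week 52 and a four-week boundary would have no function. Yet the next paragraph of 11.3 restricts reporting to attributable events only from four weeks after participation ends. Taken literally, 11.3 closes collection at week 52, gives a rule for attributable events after week 56, and gives none for the time between. It is inconsistent with itself as well as with 11.2, so the exception clause does not settle the matter.

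**Step 2: size of the gap.**

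- End of the 11.2 window: 52 + 4 = week 56.
- End of the 11.3 window: week 52.
- Difference: 56 − 52 = 4 weeks per completer.
- If all 15 complete: 15 × 4 = 60 patient-weeks.

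**Step 3: SAE follow-up after the last dose.**

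| Last dose | Under 11.3 | Under 11.2 | Difference |
|---|---|---|---|
| Week 50 | 52 − 50 = 2 weeks | 56 − 50 = 6 weeks | 4 weeks |
| Week 48 | 52 − 48 = 4 weeks | 56 − 48 = 8 weeks | 4 weeks |

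The gap is 4 weeks whichever last dose applies. It is also 4 weeks for a subject who withdraws early, if the termination visit is that subject's end of participation.

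**Step 4: number of events.** The documents give no SAE rate, so this cannot be calculated.

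**The case against.** The best counter-argument is that collecting and reporting are different activities. Section 11.2 governs what must be reported; the sentence in 11.3 governs scheduled collection. Section 11.3 itself expects attributable events to be reported after collection has closed, so it presupposes reporting outside the collection period. A site remains bound by 11.2 throughout. The literal reading is also odd: an attributable SAE at week 60 would be reported but one at week 54 would not. On this view the fault is one of drafting and few data would be lost.

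This stands in part. The reading is available, and a careful site might adopt it. But no passage states it, and a site cannot reliably report every SAE in a period in which it has been told that collection is over. The oddity of the literal reading is a reason to correct the sentence.

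Three smaller points were weighed:

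- The IRB guidelines and the trial agreement mentioned in 11.3 might state a window. They are not part of these documents and cannot be relied on to repair the protocol's text.
- The 60 patient-weeks leave out subjects who consent but are never dosed, although both windows open at consent. That is correct. The figure describes the 15 treated subjects summarised under 14.3, not everyone who consents.
- The study is small, single-centre and open-label, and its primary endpoint is untouched. This limits the consequence but does not remove the contradiction.

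**Conclusion.** The concern holds. Sections 11.2 and 11.3 set different ends to the SAE window, and 11.3 contradicts itself on the same point. The difference is 4 weeks per completer, or 60 patient-weeks if all 15 treated subjects complete and participation ends at the week 52 visit. Depending on which last dose applies, SAE follow-up after dosing is 2 or 4 weeks under one rule and 6 or 8 under the other. The number of SAEs affected is unknown and, with 15 subjects, may be zero. The effect is confined to safety ascertainment and the safety summary; the primary endpoint, alpha, power and sample size are unaffected. It should be fixed, because SAE reporting is mandatory and the correction is small.

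**What to change.** Amend the collection sentence in 11.3 so that the period ends four weeks after the subject stops study participation. This matches 11.2 and the following paragraph of 11.3, so it brings in no boundary that the protocol does not already state twice. Use the same SAE window for the safety summary when the SAP is written.

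The cost is one amended protocol sentence and one line in the SAP. The fix has a limit: since Appendix 1 schedules nothing after week 52, the extra four weeks would capture only events that become known to the site. Active capture would need an added contact, which is not part of this change.

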12 DISCONTINUATION AND REPLACEMENT OF SUBJECTS

12.1 Early Discontinuation of Study Drug

A subject may be discontinued from study treatment at any time if the subject, the investigator, or the Sponsor feels that it is not in the subject's best interest to continue. The following is a list of possible reasons for study treatment discontinuation:

- Subject withdrawal of consent (or assent)
- Subject is not compliant with study procedures
- Adverse event that in the opinion of the investigator would be in the best interest of the subject to discontinue study treatment
- Protocol violation requiring discontinuation of study treatment
- Lost to follow-up
- Sponsor request for early termination of study
- Positive pregnancy test (females)

If a subject is withdrawn from treatment due to an adverse event, the subject will be followed and treated by the Investigator until the abnormal parameter or symptom has resolved or stabilized.

All subjects who discontinue study treatment should come in for an early discontinuation visit as soon as possible and then should be encouraged to complete all remaining scheduled visits and procedures.

All subjects are free to withdraw from participation at any time, for any reason, specified or unspecified, and without prejudice.

Reasonable attempts will be made by the investigator to provide a reason for subject withdrawals. The reason for the subject's withdrawal from the study will be specified in

the subject's source documents Refer to Section 10.13 for early termination procedures.

